Overview of trial period and measurements. Primary outcomes are recorded throughout the trial period (uptake, adherence, compliance, retention, adverse events). Secondary outcomes and control measures are taken before and after the 16-week trial period.

Background and summary

Multiple myeloma (MM) is an incurable cancer of plasma cells – a type of white blood cell residing in the bone marrow. MM is the second most common haematological malignancy (Li et al., 2016), accounting for 2% of new cancer cases and 2% of cancer-related deaths in the UK each year (CRUK, 2014). MM is characterised by bone marrow plasma cells (BMPC) which produce a monoclonal [M]-protein – identical antibodies produced by one plasma cell clone. Patients also present with end organ damage (CRAB symptoms; elevated calcium, renal insufficiency, anaemia and bone lesions) as a result of plasma cell invasion of bone tissue and infiltration into organs, and blood hyperviscosity due to high circulating M-protein concentration (Kyle and Rajkumar, 2009).

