- Immune competency (e.g. phenotypic and functional analyses of peripheral blood mononuclear cells (PBMCs), serum and salivary immunoglobulins, differential blood count, infection history)
- Systemic basal inflammation levels (e.g. cytokines)
- Metabolic factors and hormone levels (e.g. glucose, insulin, growth factors)

Trial design

The trial is a pilot, single-centre, single-arm, phase I trial to evaluate the feasibility and safety of a progressive, walkingbased exercise programme for MGUS and SMM. The intervention is a progressive, individually-prescribed, walkingbased exercise programme for 16 weeks alongside usual care.

Participant eligibility criteria

The following inclusion criteria define people who are eligible for the trial:

• A diagnosis of:

SMM. Defined by IMWG criteria as absence of MM defining events or amyloidosis, AND either: (i) serum monoclonal protein (IgG or IgA) >30g/L OR urinary monoclonal protein >500mg per 24h, AND/OR (ii) clonal bone marrow plasma cells 10-60%. People with SMM, given their higher risk of progressing to MM, will initially be prioritised for enrollment into the trial, followed by people with MGUS, described next.

OR

MGUS. Defined by IMWG criteria as absence of end-organ damage attributable to the plasma cell proliferative disorder (such as hypercalcaemia, renal insufficiency, anaemia, and bone lesions [CRAB]), or amyloidosis AND BMPC <10%* AND serum M-protein <30 g/L. *Bone marrow may not be sampled in people with low-risk MGUS where there are no clinical features concerning myeloma (Rajkumar et al., 2014).

People with MGUS who present with disease progression risk factors will be prioritised for enrolment into the trial, risk factors are: non-IgG subtype, serum M protein \geq 15 g/L, and abnormal serum free light chain ratio outside normal range [0.26-1.65]. Those with three risk factors will be prioritised first, followed by two risk factors, then one risk factor, and then zero risk factors.

• Age >18 years

Sub-groups will be excluded due to safety risks:

- World Health Organisation (WHO) performance status >1
- Pregnancy
- Deemed unsafe to exercise according to the Physical Activity Readiness Questionnaire (PARQ)
- Any comorbidity that is likely to progress or be exacerbated over the course of the trial period
- Cognitive impairment deemed a risk by the healthcare team for participation in the trial (e.g. diagnosis of neurodegenerative disease)

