Quality of life: Health-related quality of life (QoL) will be assessed using the 36-item short form survey (SF-36) which includes eight domains: physical functioning; bodily pain; role limitations due to physical health problems; role limitations due to personal or emotional problems; emotional wellbeing; social functioning; energy/fatigue; general health perceptions and is validated for use with older adults. Overall QoL will be assessed using the Satisfaction with Life Scale: a 5-item questionnaire scored using a 7-point Likert scale that is validated for use in older adults.

Frailty: The International Myeloma Working Group (IMWG) frailty score is a validated questionnaire assessing aspects of frailty including comorbidities, basic activities of daily living (ADL) and instrumental ADL. The score is interpreted as fit (score = 0), intermediate-fitness (score = 1) or frail (score \geq 2). Increased frailty is associated with mortality and treatment toxicity in people with MM (Palumbo, Bringhen and Mateos, 2016). Reducing frailty prior to MM diagnosis (i.e. in people with MGUS and SMM) may delay a deterioration in frailty further along the disease continuum and therefore improve treatment outcomes and prognosis. The determinants of the frailty score are potentially responsive to exercise training, e.g. functional capacity and comorbid cardiovascular diseases.

Sleep quality: The Pittsburgh sleep quality index (PSQI) is validated to assess sleep quality and pattern in older adults. It is a 19-item questionnaire scored using a 0-3 Likert scale, with a total score >5 indicating poor sleep quality.

Fatigue: The functional assessment of chronic illness therapy (FACIT) fatigue scale is validated to assess fatigue in older adults. It is a 13-item scale scored using a 0-4 Likert scale, with a total score <30 indicating severe fatigue.

Physical activity: The international physical activity questionnaire (IPAQ) short-form is validated to assess moderate and vigorous intensity physical activity and sedentary time. Participants will be asked whether their responses are representative of the past year, e.g. whether their physical activity level has been stable or whether they can pin-point a distinct change (taking up a new exercise behaviour). This will be plotted against their past 1-year disease activity.

Resting measurements

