Strength: Upper-body strength will be reported as the average of three repetitions of a maximal grip strength test (kg) on each hand. Performance in a 30s chair stand test will be reported as the time (s) to complete five repetitions (strength) and the total number of repetitions completed (strength endurance) from a chair with a straight back and no arms.

Flexibility: Upper-body flexibility will be reported for left and right arms as the average distance (cm) between extended middle fingers in a back scratch test performed three times. Lower-body flexibility will be reported for left and right legs as the average distance (cm) between extended middle finger and the tip of the same-side toes in a chair sit-and-reach test performed three times.

Cardiorespiratory fitness

Maximal oxygen uptake (VO_{2MAX}) will be determined using a progressive incline cardiopulmonary exercise test (CPET) to volitional fatigue on a treadmill. Blood pressure and 12-lead electrocardiogram (ECG) will be recorded at rest. Treadmill speed will be kept constant, and after a 5-minute warm up at 0%, the gradient will increase by 3% every 3 minutes until fatigue (Thompson et al., 2010). Breath-by-breath gas exchange, ECG, blood pressure and oxygen saturation will be monitored continuously. A rating of perceived exertion (RPE) will be recorded at the end of each stage. A maximal effort will be verified by meeting two of four criteria: 1) heart rate (HR) within 10 bpm of age-

predicted maximum [220 – age (years)], respiratory exchange ratio \geq 1.00, RPE \geq 19 or an increment in VO₂ \leq 5 mL.kg⁻¹.min⁻¹ in response to increased gradient.

Participants unable to comply with the exercise test, for example due to a health problem raised during the exercise test (e.g. abnormal ECG or blood pressure response) or serious discomfort exercising, will discontinue involvement in the study on safety grounds. Abnormal test results will be referred to a cardiologist who will provide follow-up care and advice on the participants continued involvement in the trial. The decision on whether to repeat baseline measures will be discussed with the trial management group; e.g. if follow-up care results in a considerable delay, there may be a need to repeat baseline measures prior to commencing further trial activities.

Trial period measurements

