An important consideration for the research team when designing this study was the amount of time each participant will have to commit to the trial, which includes: 1 hour of screening and consenting, up to 5 hours of measurement visits and, finally, 32 exercise sessions (32 separate one hour visits). The screening visit has been planned to coincide with usual clinic hours at the haematology outpatients, so that people will be accustomed to the timing of this session, the familiarity of the physical environment and the practicalities of attending (e.g. parking, navigation of hospital). Trial measurement visits will be scheduled at a time of day according to the participant's availability. The exercise sessions will be run throughout the day and evenings to allow participants to choose the most suitable time for them to attend. These time considerations were made so that people who want to enrol, but are limited in terms of time availability can participate (e.g. if they have a job).

Statistics and data analysis

Sample size

The aim is to recruit 20 participants. Assuming a recruitment rate of three to four people per month and 15% drop out, we estimate the target can be reached within a suitable time-frame so the findings can be submitted for a PhD thesis (12-15 months).

There is limited information available to enable a formal sample size calculation. This pilot trial will provide preliminary data to determine that a future RCT has promise and is not futile, and to perform a sample size calculation.

Statistical analysis plan

Primary outcome measures do not lend themselves to statistical analysis. Feasibility will be reported as proportions in terms of uptake, adherence, compliance and retention. Safety will be reported as the incidence and severity of adverse events.

Secondary data will be tested for normality (e.g. Shapiro-Wilk) and in the event that some data are not normally distributed, the data will be log transformed. Descriptive statistics will be presented, and longitudinal differences and interaction effects will be identified using repeated-measures T-tests. These data will be used to inform sample size calculations in a future RCT. Incomplete data and missing values will be managed using an intention-to-treat approach with multiple imputation.

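### Paired t-tests cannot estimate the interaction effects assigned to them, and the log-only remedy cannot be applied to secondary scores that take the value zero

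*Protocol*

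**What the plan says.** Under Statistics and data analysis, Statistical analysis plan, the protocol states that "longitudinal differences and interaction effects will be identified using repeated-measures T-tests". For distribution problems it says that "in the event that some data are not normally distributed, the data will be log transformed"; no other remedy is given. The section adds that these data will inform the sample size of a future RCT.

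The Trial design section reads: "The trial is a pilot, single-centre, single-arm, phase I trial to evaluate the feasibility and safety". The note to the flow chart says: "Secondary outcomes and control measures are taken before and after the 16-week trial period". The one exception is the physical activity questionnaire, which is repeated by telephone during the 8 months after Visit 4.

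Aims and outcomes lists frailty and sleep among the secondary wellbeing indices. In the Visit 1 questionnaires, the frailty entry says "The score is interpreted as fit (score = 0", with 1 for intermediate fitness and 2 or more for frail. The sleep quality index has 19 items, each scored from 0 to 3.

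**The concern.** Two stated rules fail when followed literally.

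- An interaction needs at least two factors. Time is the only one the design provides, and the named test has no interaction term. An analyst would have to invent both the factor and the method after seeing the data, or report something that is not an interaction.
- A log transformation is impossible for any participant who scores zero. The analyst must then drop those pairs, add an arbitrary constant or leave the stated plan. For frailty the zeros are the fit participants, so dropping them would distort the estimated change.

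At stake is the quality of the secondary change estimates, and of the means and SDs handed to the RCT.

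**Working it through.** **Inputs from the protocol.** One arm (Trial design); measurement before and after (flow chart note); a t-test for both change and interaction, and log as the only remedy (Statistical analysis plan); frailty coded 0, 1, 2 or more, and sleep items from 0 to 3 (Visit 1 questionnaires). There is no planned figure to reproduce. The sample size statement is "The aim is to recruit 20 participants", without a formal calculation, and "Assuming a recruitment rate of three to four people per month and 15% drop out" gives only 20 × (1 − 0.15) = 17 completers.

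**Step 1: what the paired test estimates.** With D = follow-up − baseline for each person, t = mean(D) / (SD(D)/√n). If two groups of sizes n1 and n2 have true changes δ1 and δ2, the test targets (n1·δ1 + n2·δ2)/(n1 + n2). The group-by-time interaction is δ1 − δ2. Illustrative values, in units of the SD of change:

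| n1 + n2 | δ1 | δ2 | Paired test targets | Interaction |
|---|---|---|---|---|
| 10 + 10 | 0.8 | 0.8 | (8 + 8)/20 = 0.8 | 0 |
| 10 + 10 | 0.8 | −0.8 | (8 − 8)/20 = 0 | 1.6 |
| 5 + 15 | 0.8 | −0.8 | (4 − 12)/20 = −0.4 | 1.6 |

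The two quantities are unrelated. The first row has a large paired effect and no interaction; the second has the reverse. Running a paired test in each group does not help: it compares δ1 and δ2 each with zero, and one significant result beside one non-significant result is not a test of δ1 − δ2.

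**Step 2: is a second factor named elsewhere?** The closing paragraph on analysis allows optional subgroup splits, for example by response, but gives no model and does not link them to the interaction.

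**Step 3: the log rule on the frailty score.** ln(0) is undefined. Adding 1 maps 0, 1, 2 to 0, 0.69, 1.10. The same lumps of tied values remain, with only the spacing changed. The lowest possible sleep total is 19 items at 0, which is 0. How often zeros will occur is not stated, but a single zero at either visit blocks the rule for that pair.

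**Step 4: where the rule works.** For a strictly positive skewed assay such as M-protein, ln(follow-up) − ln(baseline) is a log ratio, and exp(mean) − 1 is a percentage change. A paired t-test on that scale is sound. Its distributional requirement concerns these paired differences.

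**Step 5: what a properly estimated interaction could deliver.** For a two-group comparison of change, the 95% CI half-width is t × SD × √(1/n1 + 1/n2). The splits are assumed, because the protocol fixes none:

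- 10 + 10: 2.10 × 0.447 = 0.94 SD
- 8 + 9: 2.13 × 0.486 = 1.04 SD
- 5 + 15: 2.10 × 0.516 = 1.08 SD
- 4 + 13: 2.13 × 0.572 = 1.22 SD

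An interval of roughly ±1 SD of change supports exploratory use only.

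**The case against.** The best defence is that little depends on this. The primary outcomes are reported as proportions and as the incidence of adverse events, the secondary outcomes are exploratory, no decision rule uses an interaction p-value, and descriptive statistics are promised separately for the RCT calculation. This stands, and it limits the severity.

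It is also true that many secondary outcomes are positive and continuous (VO2max, body mass, creatinine), so a log is at least workable for them, and for proportional changes in assays it is the right scale. In addition, a paired t-test on a difference of differences can test an interaction between two within-person factors, such as side by time. The protocol names no such factor.

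A reader might infer more than the documents support:

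- **Reach distances can be negative.** The flexibility entry describes only an "average distance (cm) between extended middle fingers in a back scratch test" and gives no sign convention.
- **Activity minutes, SF-36 domains and cytokines will contain zeros.** The protocol gives no scoring range or detection limit for them.
- **Normality is tested on raw values, so the check is wrong.** The text speaks of secondary data without saying raw values or changes. Raw values are the plausible reading, since changes can be negative and then have no log, but it is not stated. How often such a check would misfire depends on assumed distributions.
- **Significance across many tests will be the criterion for success.** The protocol sets no significance level and makes no efficacy claim from p-values, and many of its measures are listed only as examples.

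**Conclusion.** Two rules are wrong as written: a paired t-test cannot estimate a difference in change between participant groups, and a log cannot be applied to a score that includes zero. The first follows from the design and the definition of the test. The second rests on the protocol's own frailty coding and, for the possibility of zero, on its sleep item scoring. Neither depends on assumed effect sizes or variances; the values in Steps 1 and 5 are illustrations.

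The size is moderate. Exploratory secondary outcomes and the data carried to the future RCT are affected. A reader might infer that the trial's main conclusions are at risk; they are not, because the feasibility and safety summaries use neither rule.

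**What to change.** Amend the Statistical analysis plan section as follows.

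1. Delete the reference to interaction effects. Alternatively, name the factor, for example MGUS versus SMM, and estimate the between-group difference in change by regressing follow-up on baseline plus diagnosis, with a 95% CI, labelled exploratory. M-protein is part of the diagnostic definition, so for that outcome say that the estimate is conditional on baseline.
2. Fix the analysis scale for each outcome in advance. Keep the log scale, reported as percentage change, for strictly positive skewed assays.
3. For ordinal or zero-containing scores, use a rank-based paired method or a table of category shifts from baseline to follow-up, with frailty as the clear case.
4. Base any distribution check on the paired changes, on the chosen scale.
5. Report paired change with a 95% CI as the main secondary result.

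The section also plans multiple imputation. State how rank-based results will be combined across imputations, or that they and the shift tables use observed pairs only.

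The cost is a few sentences of analysis text. No new data, visits or participants are needed.

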The PhD project may utilise correlation analysis to establish whether any change in disease activity is associated to a number of mechanistic markers, and stepwise multiple regression will identify the extent to which a change in the mechanistic markers predict change in disease activity. Subgroup analysis may be performed, e.g. split to high vs. low responders or by presence of mediating variable(s) for further analysis.

Monitoring, audit and inspection

The University of Bath, as Sponsor, will monitor and conduct random audits on a selection of studies in its clinical research portfolio. Monitoring and auditing will be conducted in accordance with the Department of Health Research Governance Framework for Health & Social Care (April, 2005), and in accordance with the Sponsor's monitoring and audit policies and procedures.

Patient safety will be monitored on an ongoing basis by the research and healthcare team. A formal data monitoring committee will not be convened as this is a small single-centre pilot study. Instead, the lead researcher (PhD Student, [name]) will present an update on safety at quarterly trial management group meetings, together with the haematologist ([name]), the CI and primary PhD supervisor ([name]), secondary PhD supervisor ([name]) and patient representative(s).

Ethical and regulatory considerations

Research Ethics Committee (REC) review

Before the start of the trial, approval will be sought from an NHS REC for the trial protocol, informed consent forms, participant information sheet and recruitment letter. Substantial amendments will require review by the NHS REC will not be implemented until the NHS REC grants favourable opinion.

Public and patient involvement

A group of people diagnosed with MGUS and SMM were invited to the University of Bath on the evening of Wednesday 23rd November 2017 to discuss the proposed trial design with the research team. Discussions were held on the following topics, with feedback on each point was incorporated into the trial protocol and other trial documents:

- Proposed recruitment strategies, including invitation letters and follow-up invitation phone calls from the haematology department.
- Wording of trial documents, including the participant information sheet and consent forms.

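### Stepwise regression on about 17 change scores, with no cap on candidate markers, cannot estimate how far marker changes predict change in disease activity

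*Protocol*

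**What the plan says.** Under Statistical analysis plan, the protocol describes the mechanistic work of the PhD project. Correlation analysis is optional and is meant to establish "whether any change in disease activity is associated to a number of mechanistic markers". The next step is worded as definite: "stepwise multiple regression will identify the extent to which a change in the mechanistic markers predict change in disease activity". The paragraph adds: "Subgroup analysis may be performed, e.g. split to high vs. low responders", with a split by mediating variables as an alternative.

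Under Sample size: "The aim is to recruit 20 participants", and "Assuming a recruitment rate of three to four people per month and 15% drop out". No power calculation supports the number: "There is limited information available to enable a formal sample size calculation". Trial design states: "The trial is a pilot, single-centre, single-arm, phase I trial".

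Aims and outcomes names three disease-activity measures (M-protein, serum free light chains, beta-2 microglobulin) and makes none of them the main one. The markers are given as examples within families. The immune family alone covers "phenotypic and functional analyses of peripheral blood mononuclear cells (PBMCs), serum and salivary immunoglobulins, differential blood count, infection history". Cytokines, glucose, insulin and growth factors follow, and Trial treatment adds body composition as a fourth hypothesised mechanism.

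**The concern.** Stepwise regression searches the candidates for those that happen to correlate best with the outcome in this sample, then reports fit and p-values as if no search had taken place. With few observations and many candidates, the reported R² is too high and the p-values too small. The protocol nevertheless assigns this method the job of measuring how strongly markers predict disease activity, which is the quantity that selection distorts most.

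This is a stated choice of method, not a detail left for later. A separate analysis plan could fix the marker list and entry thresholds, but stepwise selection in about 17 people would still be unsuited to the purpose.

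The responder split raises a related problem under one reading. If response means change in disease activity, the groups are formed from the outcome itself, and a single before-and-after difference mixes any true response with assay error and biological fluctuation.

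At stake is the credibility of the mechanistic conclusion: a marker could be reported as explaining a third to a half of the variation in disease-activity change when it explains none.

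**Working it through.** **Inputs from the protocol.** 20 recruited and 15% drop-out: 20 × (1 − 0.15) = 17 completers. The plan gives no error rate or power for the regression, so there is no figure of its own to reproduce.

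**Assumed inputs.** Candidate count k from 5 to 30; entry p<0.05 and removal p>0.10; normal data; no true association; markers either independent or equally correlated at 0.5.

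**Chance of at least one false predictor.** The procedure selects something whenever at least one marker has a single-marker p below 0.05. For independent markers this probability is 1 − 0.95^k. Simulation (3000 null trials per setting, n = 17, one outcome) gives:

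| k | 1 − 0.95^k | Simulated, independent | Simulated, correlation 0.5 | Median R² when something is selected (independent / 0.5) |
|---|---|---|---|---|
| 5 | 23% | 22% | 18% | 0.312 / 0.309 |
| 10 | 40% | 41% | 29% | 0.344 / 0.345 |
| 15 | 54% | 53% | 37% | 0.383 / 0.400 |
| 20 | 64% | 65% | 45% | 0.476 / 0.467 |
| 30 | 79% | 79% | 55% | 0.593 / 0.537 |

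A separate repeat at k = 10, 20 and 30 gave 38%, 62% and 78% for independent markers (median R² 0.36, 0.48, 0.57) and about 31%, 43% and 50% at correlation 0.5. The rounded ranges in the conclusion cover both runs.

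**Why R² is inflated even with few candidates.** To enter first at p<0.05 with n = 17 (15 degrees of freedom, critical t = 2.131), a marker needs r² of at least t²/(t² + 15) = 4.54/19.54 = 0.23. Whatever enters therefore arrives with an apparent R² of at least 0.23, even when the true value is 0.

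**Sensitivity.**
- Analysed n of 20, if multiple imputation restores the full sample (independent markers): selection 42% at k = 10 and 64% at k = 20; median R² 0.288 and 0.402.
- Looser entry rules (n = 17, k = 10, independent): 66% at p<0.10 and 82% at p of about 0.157.
- All three disease-activity measures modelled in turn (assumed correlated 0.5), at least one false predictor in any: 60–75% at k = 10 and 78–94% at k = 20, the lower value for correlated markers. The protocol does not say whether it would do this.

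**Precision of a single prespecified correlation.** Fisher's z gives a 95% half-width around r = 0 of tanh(1.96/√(17 − 3)) = tanh(0.524) = 0.48.

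**The case against.** The strongest reply is that the number of candidates is unknown. A reader might infer that the plan will usually find predictors in noise. The protocol does not support this: it gives no marker count. For one outcome at p<0.05, the rate passes one half only at k = 14 even with independent markers (1 − 0.95^14 = 51%), and related immune cells, cytokines and hormones are unlikely to be independent. At correlation 0.5 the rate is only about 50–55% even with 30 candidates. This part of the objection stands, so the false-selection rate has to be given as a range tied to assumed counts. The R² inflation does not depend on it: the median is about 0.31 even at k = 5.

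A second reply is that the responder split is optional and does not say response in what. That also stands. A split on fitness response would not condition on the disease outcome, so the criticism applies only if disease activity is meant. Nor is a single before-and-after pair necessarily all the data. Screening gives access to disease-activity history, the Visit 1 questionnaire section refers to the past year's values, and Follow-up measurements refers to routine monitoring after Visit 4. The protocol does not say that these would define response, and Background and summary notes that low-risk MGUS is monitored only when symptoms arise.

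A third reply is that this is exploratory work inside a pilot. The aims are indeed preliminary, but the paragraph carries no exploratory label and claims to identify an extent of prediction. A reader might also infer that spurious markers would be carried into the future RCT. The protocol says that pilot data will inform the RCT's design and power, including for mechanisms, but not that the stepwise results will choose its markers or groups.

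**Conclusion.** The concern holds as a fault in a stated secondary analysis and should be corrected. Stepwise regression on 17 to 20 change scores cannot estimate how far marker changes predict disease-activity change. Under pure noise with one outcome, it selects at least one marker in about 20% of trials with 5 candidates, 30–40% with 10, 45–65% with 20 and 50–79% with 30, and the median R² when something is selected is about 0.3 to 0.6 against a true value of 0. These figures rest on assumed candidate counts, entry and removal at 0.05 and 0.10, normal data, and marker correlation between 0 and 0.5.

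The responder point is conditional on response meaning disease activity measured by a single before-and-after change. Nothing here touches the primary feasibility and safety outcomes, which are reported as proportions and adverse-event incidence.

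**What to change.** In Statistical analysis plan:

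- Replace the stepwise regression with a short list of markers fixed before the data are seen, for example one for each hypothesised mechanism in Trial treatment (immune, inflammatory, metabolic, body composition).
- Name one main disease-activity measure. Report the correlation of each listed marker's change with continuous change in that measure, with a 95% CI, whatever the result, and label it hypothesis-generating. State the expected precision: about ±0.48 around r = 0 at n = 17.
- Report the remaining disease-activity measures and markers descriptively.
- Analyse disease-activity change as a continuous variable rather than by a responder split.

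Four correlations still carry a chance of 1 − 0.95^4 = 19% that at least one interval excludes 0 by chance if the markers are independent, hence the label. The gain is that every estimate is reported, so none is inflated by selection.

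The cost is a change of wording and fewer markers formally tested in the thesis. No new data are needed.
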